10.6.4 Factors Associated with AF Disease Progression

To analyze this secondary endpoint, conditions that may be associated with disease progression will be assessed at baseline and throughout the 3-year follow-up period.

Cox proportional hazards models will be used to examine the associations of baseline-variables with time to disease progression. Time to disease progression is referring to time to persistent AF/AT (primary endpoint) in this section. The following baseline variables will be investigated:

- gender
- age (categories: <75 years, ≥75 years)
- LA size (Parasternal long axis view from transthoracic echocardiogram) (not large: ≤ 55mm/large: >55mm)
- AF duration (continuous)
- number of AF events in 6 months prior to trial
- heart failure (yes vs. no) (as specified in HATCH score component)
- hypertension (yes [past or present] vs. no)
- hyperlipidemia/dyslipidemia (yes [past or present] vs. no)
- renal insufficiency (yes [past or present] vs. no)
- diabetes (yes vs. no)
- dementia (yes vs. no)
- previous TIA or stroke (yes vs. no) (as specified in HATCH score component)
- previous COPD (yes vs. no)(as specified in HATCH score component)

For the baseline variables, in a first step, single covariate Cox models including the

respective covariate, the treatment factor and the covariate*treatment interaction term will be fitted. In a second step, a multivariate Cox model will be fitted including the treatment factor and all covariates plus covariate*treatment interaction terms for which either the covariate or the interaction term had been associated with time to disease progression with a p-value < 0.2 in the single variate model. The Stepwise option of PROC PHREG will be used for model selection, setting the level for covariates to enter and to stay in the model to 0.05.

These analyses will be performed in the ITT and PP populations (with fixed treatment effect in the PP population).

Moreover, in the PP population the following analysis will be performed modelling the treatment effect as time-dependent covariate and additionally including baseline covariates: in a first step, single covariate Cox models including the respective covariate and the treatment factor (as time-dependent covariate) will be fitted. In a second step, a multivariate Cox model will be fitted including the treatment factor (as time-dependent covariate) and all covariates which had been associated with time to disease progression with a p-value < 0.2 in the single variate model. The Stepwise option of PROC PHREG will be used for model selection, setting the level for covariates to enter and to stay in the model to 0.05.

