Variables such as patient age and the presence of comorbidities must also be considered when determining rates of AF progression. Age is the most well-studied and consistently significant factor associated with AF progression. Two studies quantifying the increased risk of AF progression for each decade of age found 40% and 82% increases in risk, respectively. Left atrial (LA) size/volume and hypertension have been frequently studied, with LA volume somewhat more likely to be significant in univariate analyses but not significant in predictive multivariate models. A study from Japan focused on LA wall thickness as a marker of structural remodeling; the authors suggested it to be a stronger predictor of AF progression than LA volume in their cohort of patients. Valvular disease and heart failure were each reported as significant in 4 studies using multivariate models. Valvular disease (univariate or multivariate analyses) and heart failure have also been reported as linked to AF progression. In one study, a composite score (HATCH score), which incorporates hypertension (1 point), age >75 years (1 point), stroke/TIA (2 points), COPD (1 point), and heart failure (2 points), was found to be strongly predictive of AF progression; patients with a moderate to high HATCH score (2-7 points) faced a 25-40% annual risk of AF progression, as compared to below 10% for patients scoring 0 or 1.

In another AF study, the HATCH score was not found to be predictive of AF progression among patients treated by catheter ablation.

The predictive power of patient age seems sensible in the context of AF as a self-perpetuating arrhythmia with interdependent mechanisms. Animal studies of atrial remodeling have proposed that “AF begets AF.” Experimental induction of sustained AF in dogs and in goats support this model. Changes to atrial architecture (fibrotic disorganization and increased atrial size) have also been documented in these animal models. With animal models supporting the concept that “AF begets AF”, similar progression, though not well-studied, is thought to occur in humans, which may warrant treatment (either with AADs or catheter ablation) to delay or prevent such progression and/or changes.

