### 9.3 Study Inclusion Criteria

1. Patients with recurrent paroxysmal AF for at least 2 years, with  $\geq 2$  episodes over the last 6 months;
2. HATCH Score of at least  $\geq 1$  and  $\leq 4$ .c
3. Eligible for catheter ablation and for anti-arrhythmic or rate control medications, after having failed at least 1 but no more than 2 prescribed drugs (either anti-arrhythmic or rate control drug).
4. Age 60 years or older.

---

c Hypertension (+1); Age >75 years (+1); previous TIA or Stroke (+2); COPD (+1); Heart failure - including systolic or diastolic heart failure (+2).

5. LA diameter  $\leq$  55mm by TTE.
6. LV ejection fraction  $\geq$  50% when in sinus rhythm or LV ejection fraction  $\geq$  35% when in AF.

NOTE: For patients entering the study in AF with an ejection fraction  $\geq$  35% and  $<$  50%; the ejection fraction should be re-checked when in sinus rhythm. In case the ejection fraction is  $\geq$  50% the subject can continue in the study.

7. Patient signed the Informed Consent Form and is able and willing to comply with protocol requirements, including all baseline and follow- up testing.

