#### **13.12.4 Factors Associated with AF Disease Progression**

To analyze this secondary endpoint, conditions that may be associated with disease progression will be assessed at baseline and throughout the 3-year follow-up period. These targeted parameters include: LA size at baseline and subsequent increase above baseline size; age  $\geq 60$  years; HATCH score at baseline and subsequent increase above baseline score; hypertension; NYHA Functional Classification of heart disease; diabetes; hyperlipidemia/dyslipidemia; renal insufficiency; and, dementia. A Cox proportional hazards model will be performed to examine the associations of time with disease progression. To document pre-existing diseases, measurable baseline parameters will include age, gender, LA size, AF duration, NYHA Functional Classification of heart disease, HATCH score, blood pressure, lipid profile, renal function and the presence of diabetes and/or dementia. The Cox proportional hazards model will also be used to examine time-varying covariates, based upon each follow-up visit and either as a new onset disorder or a worsened diagnosis since a previous assessment. These analyses will include all follow-up assessments throughout the 3-year study period and measurable parameters will include: LA size; HATCH Score; blood pressure; NYHA Functional Classification of heart disease; diabetes; lipid profile; renal function and, dementia. All analyses will control for treatment assignment. Any significant interactions between treatment effect(s) and covariates will also be examined.

Univariate analysis will be performed to screen for significant factors associated with disease progression at p-value  $<0.2$ . Then multivariate analyses will be performed to identify any factors associated with disease progression at p-value  $<0.05$ . Model selection methods (e.g., Akaike Information Criteria [AIC], stepwise) will be applied to identify the best set of factors linked to disease progression. The identification of relevant associations provides additional characterization and interpretation of the primary effectiveness outcome. These analyses will be performed in both the ITT and PP populations.

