### 13.16 Summary of Secondary Endpoints

#### Secondary Endpoints – Effectiveness

Effectiveness endpoint 1: Rate and time to persistent AF/AT at 1 year and 2 years, rate of persistent AF/AT at 3 years by number of ablations at 3 years.
Analysis Population: ITT and PP
Analysis Method: KM curve

Effectiveness endpoint 2: Number of repeat ablations and new AAD drugs per subject throughout 3 years follow-up.
Analysis Population: ITT and PP
Analysis Method: Descriptive statistics

Effectiveness endpoint 3: Rhythm (% subjects in sinus rhythm, % subjects with recurrent AF) throughout 3 years follow-up.
Analysis Population: ITT and PP
Analysis Method: Descriptive statistics

Effectiveness endpoint 4: Subject age ( $\geq 60$ years); gender; and comorbidities possibly associated with disease progression, at baseline and throughout the 3-year follow-up period: abnormally large LA; HATCH Score $\geq 1$ ; hypertension; Class 1 – 4 inclusive of NYHA Functional Classification of heart disease; hyperlipidemia/dyslipidemia; diabetes; renal insufficiency; and, dementia.
Analysis Population: ITT and PP
Analysis Method: Univariate and multivariate Cox proportional hazards model

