2.2 Efficacy, Safety and Health Economic Endpoints

2.2.1 Efficacy Endpoints

The primary efficacy endpoint is the time to persistent AF/AT (excluding isthmus-dependent atrial flutter) at 3 years. According to the protocol, persistent AF/AT is defined as AF/AT lasting longer than 7 consecutive days or requiring termination by cardioversion after 48 hours.

Secondary efficacy endpoints are:

- Rate and time to persistent AF/AT at 1 year and 2 years, rate of persistent AF/AT by number of ablations at 3 years
- Number of repeat ablations and new anti-arrhythmic drugs (AAD) per subject throughout 3 years follow-up

- Rhythm (% subjects in sinus rhythm (SR), % subjects with recurrent AF/AT) throughout 3 years follow-up
- Factors associated with AF disease progression
 - Gender
 - Age
 - Left atrium (LA) size
 - HATCH score (score based on the five components: Hypertension, Age 75 years or older, Previous transient ischemic attack or stroke, Chronic obstructive pulmonary disease, and Heart failure)
 - Blood pressure
 - NYHA functional classification of heart disease
 - Presence of diabetes
 - Presence of hyperlipidemia or dyslipidemia
 - Presence of renal insufficiency
 - Presence of dementia

In addition, an alternative definition of the primary and the first secondary endpoint will be investigated based on the consensus statement of the HRS (Heart Rhythm Society, 2017). According to the HRS consensus statement 2017, persistent AF/AT is defined as continuous AF/AT that is sustained beyond 7 days.

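### The progression-factor Cox models in SAP 10.6.4 omit three factors the SAP itself lists (HATCH score, NYHA class, blood pressure) and reduce age to a split at 75, so this secondary endpoint is only partly answered

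*SAP*

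**What the plan says.** SAP 2.2.1 lists ten factors for this secondary endpoint: gender, age, LA size, HATCH score, blood pressure, NYHA class, diabetes, hyperlipidemia or dyslipidemia, renal insufficiency and dementia. Protocol 13.12.4 describes the Cox analysis in similar terms: "measurable baseline parameters will include age, gender, LA size, AF duration, NYHA Functional Classification of heart disease, HATCH score, blood pressure". The summary of effectiveness endpoint 4 in Protocol 13.16 also names HATCH and NYHA class, with "Analysis Method: Univariate and multivariate Cox proportional hazards model".

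SAP 10.6.4 then gives the baseline variables that will actually be modelled. There are thirteen, and HATCH score, NYHA class and blood pressure are not among them. Age appears as "age (categories: <75 years, ≥75 years", while AF duration stays continuous. Each variable is first fitted alone with treatment and a treatment interaction. Variables that pass p<0.2 on either term go into a multivariate model with stepwise selection at 0.05.

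SAP 5.1 says that this analysis was reduced and that some supporting models were removed. It does not say that any listed factor was dropped.

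On the HATCH age item, SAP 2.2.1 has "HATCH score (score based on the five components: Hypertension, Age 75 years or older", whereas the footnote to the inclusion criteria in Protocol 9.3 has "Age >75 years (+1".

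**The concern.** A reader who takes the endpoint from SAP 2.2.1 will expect results for all ten factors and will find no model for three of them. HATCH matters most. It sets eligibility, and Protocol 5.1 cites one study in which it predicted progression strongly and another in which it did not among ablated patients. That contrast makes a score-by-treatment interaction a natural question, and the single-covariate models already carry such a term for every variable they include.

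Protocol 5.1 also treats age as the best-studied and most consistent predictor, and it gives the effect per decade: "Two studies quantifying the increased risk of AF progression for each decade of age found 40% and 82% increases in risk". A single cut at 75 cannot estimate an effect per decade, and it weakens the test of the factor with the most prior support. Age is then less likely to pass the p<0.2 screen and reach the multivariate model.

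**Working it through.** **Factor lists side by side**

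| SAP 2.2.1 factor | In the Cox list of SAP 10.6.4? |
|---|---|
| Gender | Yes |
| Age | Yes, two categories at 75 |
| LA size | Yes, two categories at 55 mm |
| HATCH score | No; hypertension, age, TIA/stroke, COPD and heart failure enter separately |
| Blood pressure | No; hypertension yes/no |
| NYHA class | No; nearest is heart failure yes/no |
| Diabetes, lipids, renal insufficiency, dementia | Yes, each yes/no |

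Seven of the ten are in the list. The time-dependent-treatment models at the end of SAP 10.6.4 and planned Tables 14.2.10.1 to 14.2.10.4 do not add the other three. Blood pressure and NYHA class appear only in listings 16.2.19 and 16.2.20. HATCH has listing 16.2.21 and a baseline description in SAP 9.3.

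**Planned events**

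The operating-characteristics table in SAP 10.4 has 28 events at the final look. The effect size is −ln[ln(0.95)/ln(0.85)] = 1.153 (the plan prints 1.1541). The Schoenfeld formula for 1:1 allocation, one-sided 0.025 and 85% power gives 4 × (1.960 + 1.036)² / 1.153² = 27.004, rounded up to 28. The plan's count is reproduced.

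**What the age split keeps**

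The documents do not give an age distribution. I assume a truncated normal on 60 to 88 with underlying SD 6 and underlying mean 66, 68 or 70. Let r be the correlation between age and the indicator for 75 or older. For a log-linear age effect, the split keeps about r² of the information. Approximate test statistics with 28 events are:

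- continuous age: z = √28 × ln(HR per decade) × SD/10
- split: r × z
- power: Φ(z − 1.96) + Φ(−z − 1.96)

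| Underlying mean | 66 | 68 | 70 |
|---|---|---|---|
| SD after truncation | 4.8 | 5.1 | 5.4 |
| Share aged 75 or older | 8% | 13% | 21% |
| r | 0.61 | 0.68 | 0.74 |
| r² (information kept) | 0.37 | 0.46 | 0.55 |
| HR 1.82: z, continuous / split | 1.51 / 0.92 | 1.61 / 1.10 | 1.70 / 1.26 |
| HR 1.82: power, continuous / split | 0.33 / 0.15 | 0.37 / 0.20 | 0.40 / 0.24 |
| HR 1.40: z, continuous / split | 0.85 / 0.52 | 0.91 / 0.62 | 0.96 / 0.71 |
| HR 1.40: power, continuous / split | 0.14 / 0.08 | 0.15 / 0.09 | 0.16 / 0.11 |

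The two hazard ratios are the per-decade effects quoted in Protocol 5.1. At the SAP's own screen of p<0.2 (1.282 in place of 1.96) and HR 1.82, the chance that the age term passes is 0.59–0.66 continuous against 0.37–0.50 split. The formula ignores the treatment interaction that SAP 10.6.4 puts in each single-covariate model, so these figures show the relative loss rather than exact power.

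**Room for extra covariates**

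- Now: 28/13 = 2.2 events per candidate, or 28/26 = 1.1 counting interactions.
- With all three added as multivariate candidates: 28/16 = 1.75, or 28/32 = 0.9.
- With NYHA class and blood pressure only, one term each: 28/15 = 1.9.

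**HATCH age item**

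The two wordings differ only for subjects aged exactly 75. Under the same assumed distributions that is about 2% to 5% of subjects, or 7 to 15 of 322.

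**The case against.** The strongest reply is that little of substance is missing. Seven of the ten factors are modelled, and so are all five HATCH components. Blood pressure is represented by hypertension, which is how Protocol 13.16 itself states it. SAP 5.1 does announce a reduction. This stands against a stronger reading, that the endpoint cannot be answered at all. The documents do not support that reading, because most factors are still tested and only NYHA class has no close counterpart. It does not remove the gap. Protocol 13.12.4 lists hypertension and blood pressure separately, five separate terms do not test the weighted score, and removing models is not the same as removing factors that SAP 2.2.1 still lists.

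On age, the protocol does not require a continuous term. Protocol 13.12.4 and 13.16 mention age of at least 60, which is constant under the inclusion criteria, so a cut at 75 is at least informative. That is fair, and the case for continuous age is about efficiency, not about a departure from the protocol. Power is also low on either scale, the 28 events come from a table the SAP calls an example, and SAP 5.1 says the study stopped early. All of this stands.

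A reader might also infer that the age covariate in SAP 10.6.4 contradicts the protocol's HATCH definition. It does not. Unlike heart failure, TIA/stroke and COPD, age is not labelled there as a HATCH component. The conflict is between SAP 2.2.1 and the protocol. SAP 8.3 derives no HATCH score and no planned model uses one, so no planned model changes. Nor are five components and five interactions fitted together by design: they are screened one at a time.

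Finally, adding covariates could worsen overfitting. That holds for the multivariate step, and the fix has to respect it.

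**Conclusion.** The point holds as an incomplete and inefficient analysis of an exploratory secondary endpoint. HATCH score, NYHA class and blood pressure are listed as factors but appear in no model, and the SAP does not explain why. The age split keeps about 37% to 55% of the information in age. At 28 events and HR 1.82 per decade it lowers approximate power from 0.33–0.40 to 0.15–0.24, and at HR 1.40 from 0.14–0.16 to 0.08–0.11. These figures rest on the assumed age distribution, a log-linear age effect and the planned event count. The comparison of the factor lists rests on no assumption. The primary analysis is not affected. The HATCH age boundary is a minor wording matter.

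**What to change.** In SAP 10.6.4:

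- Enter baseline age as a continuous term per 10 years in place of the two categories. It uses one degree of freedom, as the split does.
- Add baseline HATCH score (per point), NYHA class and baseline blood pressure to the single-covariate models, with the treatment interaction already specified there.
- State that HATCH does not enter the multivariate step, where its components are candidates. State also whether NYHA class and blood pressure may go forward. Keeping all three at the single-covariate step leaves the multivariate step at 13 candidates.
- Label the whole analysis as exploratory.

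If the sponsor prefers not to add models, SAP 2.2.1 and 10.6.4 should at least be aligned, and SAP 5.1 should say which factors were dropped and why.

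Separately, reconcile the wording of the HATCH age item between SAP 2.2.1 and the protocol.

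The cost is a change of SAP wording and three more single-covariate models, run on data that the assessment schedule already collects at baseline. The downside is three more exploratory results on few events.

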3.2 Selection of Study Population

This is a post-marketing study in subjects with Paroxysmal AF (PAF). Key inclusion criteria identified in the protocol are:

- Subjects with recurrent paroxysmal AF for at least 2 years, with ≥ 2 episodes over the last 6 months
- HATCH Score of at least ≥ 1 and ≤ 4
- Eligible for catheter ablation and for anti-arrhythmic or rate control medications, after having failed at least one but no more than 2 prescribed drugs (either anti-arrhythmic or rate control drug)
- Age 60 years or older
- LA diameter ≤ 55 mm by Transthoracic Echocardiography (TTE)
- Left ventricle (LV) ejection fraction $\geq 50\%$ when in sinus rhythm or LV ejection fraction $\geq 35\%$ when in AF
- Subject signed the Informed Consent Form and is able and willing to comply with protocol requirements, including all baseline and follow-up testing.

For the complete list of in- and exclusion criteria see the CTP, Sect. 9.3 and 9.4.

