5. CHANGES TO PLANNED ANALYSIS

5.1 Changes for the final analysis

As the study was terminated early, without having met primary effectiveness or futility criteria at the most recent interim analysis, it is not fully obvious which alpha level to use for the primary efficacy analysis. However as the number and time points of the interim analyses had not been fixed in advance, it was decided to spend all alpha remaining for the final analysis, in other words to spend what is left from the total alpha. Moreover, after further discussion, it has been decided to update the calculation of the primary endpoint to use procedure date as start date for time to event calculation rather than randomization date (see section 8.3).

It also was decided to delete some of the analyses originally planned in the protocol:

- For secondary endpoint “factors associated with AF disease progression”, only the main analyses will be performed, and some of the supporting models were deleted
- Analysis of site heterogeneity will not be performed

Moreover, a sensitivity analysis for the primary endpoint and first secondary endpoint was added, using an alternative definition for the primary endpoint based on the consensus statement of the HRS (Heart Rhythm Society, 2017).

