9.2 Protocol Violations and Deviations

Protocol deviations are captured in the CRF on a specific protocol deviation CRF page.

Incidences of all protocol deviations reported in the CRF will be summarized by protocol deviation code. A listing of these protocol deviations will also be included.

Each protocol deviation entered to the eCRF will be classified by the sponsor into major and minor from study conduct perspective. The sponsor assessment will be included in the data base extract.

A major deviation will not automatically lead to exclusion of a subject from PP population. Generally, it is planned to exclude a subject only from PP population in case of a major protocol deviation related to inclusion or exclusion criteria. To make a final decision, the sponsor will review all cases with major deviations individually and decide which subjects to exclude from PP population. The sponsor will provide a list of subjects to be excluded from PP population. The sponsor review will be completed before DB lock..

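### Baseline LA size is split at 55 mm, the eligibility ceiling, so the covariate does not vary among subjects who meet inclusion criterion 5

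*SAP*

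**What the plan says.** SAP 3.2, restating protocol inclusion criterion 5, requires "LA diameter ≤ 55 mm by Transthoracic Echocardiography (TTE"). SAP 10.6.4 lists the baseline variables for the models of time to persistent AF/AT, and codes LA size as "LA size (Parasternal long axis view from transthoracic echocardiogram) (not large: ≤ 55mm/large: >55mm"). The same list keeps another measurement on its natural scale: "AF duration (continuous").

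The binary LA variable is used in two sets of models:

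- **Fixed treatment, ITT and PP.** The first-step model has the "respective covariate, the treatment factor and the covariate*treatment interaction term will be fitted". A variable goes forward if it or its interaction reaches p<0.2; stepwise selection at 0.05 follows.
- **Time-dependent treatment, PP only.** Here the first step is "single covariate Cox models including the respective covariate and the treatment factor (as time-dependent covariate) will be fitted".

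On the PP population, SAP 9.2 says the general plan is to "exclude a subject only from PP population in case of a major protocol deviation related to inclusion or exclusion criteria". It also says "A major deviation will not automatically lead to exclusion of a subject from PP population", because the sponsor decides case by case.

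Protocol 13.12.4 names baseline LA size and later enlargement as factors, and protocol 13.16 speaks of an abnormally large LA. Neither gives 55 mm as an analysis cut.

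**The concern.** The cut-point of the covariate is the upper limit for entering the trial, in the same modality and unit. The upper category can therefore hold only two kinds of subject: those enrolled in deviation from criterion 5, and those whose parasternal long-axis value differs from the diameter used at screening (criterion 5 names no echocardiographic view). Neither is a planned contrast between smaller and larger atria.

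LA size is a named factor of the secondary endpoint on AF progression in both documents. As coded, the models either give no LA result or give one driven by a handful of unusual subjects. Variation below 55 mm, where essentially the whole trial population lies, is discarded. A report that LA size was not selected could be misread as evidence that it does not matter.

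**Working it through.** The documents give no figure for LA size to reproduce. The main check is logical, and the arithmetic after it only shows scale.

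**1. Logic.** Eligible: diameter ≤55 mm. Coded large: diameter >55 mm. The two sets do not overlap. If all analysed diameters meet the criterion, the share p coded large is 0. The Cox information for a binary covariate is about D·p·(1−p), where D is the number of events. With D = 28 this is 28·0·1 = 0. A trial fit on 322 simulated subjects, all at or below 55 mm, confirmed it: the matrix of LA, treatment and their product had rank 1 of 3, and the fit failed as singular.

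**2. A few subjects above 55 mm.** Inputs: N = 322 (SAP 6) and D = 28 (final look in the SAP 10.4 table). The number k above 55 mm is assumed.

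- SE(log HR) = 1/√(D·p·(1−p)), with p = k/322 and no interaction in the model.
- P(no event among the k) = (1 − 28/322)^k, if they carry average risk.

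| k | SE(log HR) | P(no event) |
|---|---|---|
| 1 | 3.40 | 0.91 |
| 3 | 1.97 | 0.76 |
| 5 | 1.53 | 0.64 |
| 10 | 1.09 | 0.40 |

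For example, k = 3 gives p = 0.00932 and 1/√(28 × 0.00932 × 0.99068) = 1.97.

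The fixed-treatment first-step model also contains the interaction, so its LA coefficient is estimated in the reference arm alone. The planned 3-year risks of 5% and 15% (SAP 6) split the 28 events 7:21. With k = 10, five per arm, p = 5/161 and:

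- control as reference: SE = 1/√(21 × 0.0311 × 0.9689) = 1.26;
- test as reference: SE = 1/√(7 × 0.0311 × 0.9689) = 2.18;
- chance of an event in both arms, needed for a finite interaction estimate: [1 − (1 − 7/161)^5] × [1 − (1 − 21/161)^5] = 0.199 × 0.503 = 0.10.

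The trial stopped early (SAP 5.1: "As the study was terminated early, without having met primary effectiveness or futility criteria at the most recent interim analysis"), so D may not be 28. With 15 events (look 4 of the same table), the no-interaction SE for k = 1 to 10 is 4.64 to 1.49, and P(no event) is 0.95 to 0.62.

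**3. The same data with LA continuous.** Assumed SD is 4 to 6 mm, with the same 7:21 split. SE per 5 mm = 5/(SD·√events).

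| Term | Events | SE, SD 4 mm | SE, SD 6 mm |
|---|---|---|---|
| LA, control reference | 21 | 0.27 | 0.18 |
| LA, test reference | 7 | 0.47 | 0.31 |
| LA × treatment | both arms | 0.55 | 0.36 |
| LA, no interaction | 28 | 0.24 | 0.16 |

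The interaction SE is the root of the sum of the two squared arm SEs. The last row has the form of the PP time-dependent model, if all 28 events stayed in PP.

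Two-sided power for the LA coefficient, with the same assumed HR per 5 mm in both arms, SD 4 to 6 mm:

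| Assumed HR | Control ref., p<0.2 | Control ref., p<0.05 | Test ref., p<0.2 | Test ref., p<0.05 |
|---|---|---|---|---|
| 1.2 | 30–40% | 10–17% | 23–27% | 7–9% |
| 1.3 | 39–57% | 16–30% | 27–34% | 9–13% |
| 1.5 | 58–83% | 32–61% | 35–51% | 14–25% |

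Because the screen passes on either term, the pass rate at HR 1.5 is 67–88% (control reference) or 44–60% (test reference). With no LA effect it is 33% or 27%. These rates come from 2,000,000 draws of the two arm coefficients.

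**The case against.** **The information may survive elsewhere.** SAP 5.1 says some supporting models for this endpoint were dropped but does not name them. Protocol 13.12.4 also planned summaries of baseline and follow-up LA size, change from baseline and a between-group comparison, and the SAP allows labelled exploratory work. In part this stands: the loss is of a prespecified association between LA size and progression, and the data can still be analysed. But the protocol summaries do not relate LA size to progression, and no SAP section or planned table contains another LA-size model.

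**Some subjects may exceed 55 mm.** True, and in PP a discordant reading without a deviation could remain. Such subjects still give no information about variation within the eligible range.

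**The illustration favours the fix.** The no-event chances assume average risk above 55 mm, while the continuous coding is judged under a real effect. This is fair. If those subjects had an assumed 2- to 3-fold hazard, the no-event chance for k = 10 falls from 40% to 16–7%, and the chance of an event in both arms rises from 10% to 27–43%. The SEs in the first table of the working also come from a model without interaction, which understates the problem in the SAP's first-step model. None of this alters the logical point.

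**It is minor.** LA size is one of 13 covariates in a screening exercise on few events, and power stays modest after the change. That limits the consequence but does not justify a covariate that cannot vary by design.

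**Conclusion.** The point holds. A stated eligibility rule makes a named factor of a secondary endpoint constant for every subject who meets it. If nobody exceeds 55 mm, the SAP 10.6.4 models yield no LA hazard ratio. If a few do, the result depends on those few subjects and a null finding is uninformative.

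This conclusion rests only on the two stated thresholds. The sizes shown depend on assumed counts above 55 mm, an assumed SD and assumed hazard ratios, and on planned event numbers that early termination may have changed. The primary log-rank analysis is unaffected. It should be corrected, but it does not threaten the trial's main conclusion.

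**What to change.** In SAP 10.6.4, replace the LA entry with: LA size (baseline parasternal long-axis diameter from TTE, continuous; hazard ratio per 5 mm). State the reference arm for the interaction models. If a category is also wanted, prespecify a cut inside the eligible range before outcomes by LA size are examined.

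The cost is one line of text, and the measurements are already collected (listing 16.2.30). There are four drawbacks:

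- a continuous term assumes a log-linear effect;
- power stays modest;
- the LA coefficient in the interaction model depends on the reference arm, which the SAP does not name;
- the trial is open-label, has had interim looks and has stopped, so the change should be dated and, if made after database lock, labelled post hoc.

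The baseline dementia covariate in the same list deserves the same check, since a footnote to protocol 10.2 says dementia at baseline precludes enrolment.
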